The proposed methodology for the clinical trial will be validated by the DSMB so that it does not jeopardise the safety of subjects, in particular relating to the inclusion and randomization methods.

- Validation of tolerance monitoring methods:
 - o nature of the evaluated parameters
 - o frequency of the evaluations, consultation schedule
- Validation of termination criteria:
 - o criteria for terminating a subject's participation for tolerance reasons

- criteria for the temporary or permanent termination of the research (leading to the establishment of certain recommendations ("stopping rules"))
- Modification of the protocol and recommendations:
In light of the analysis of tolerance data for the research, the DSMB can, when applicable: propose substantial modifications in order to modify certain data, in particular relating to the protocol (inclusion and non-inclusion criteria, monitoring, additional exams, etc.). Likewise the DSMB can issue any recommendations it deems useful in order to best ensure the safety of the research subjects and to maintain a favourable benefit-risk balance throughout the research.

Definition of the DSMB's operating methods:

- meeting types (open session, then closed sessions) and schedule
- desired methods and format of SAE notification from the sponsor to the DSMB

The DSMB appoints its chairman at the first meeting.

The sponsor retains decision-making authority. When applicable, the sponsor delivers its decision, with justification, and DSMB reports to the Competent Authority (ANSM) and the CPP.

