In light of the results obtained for the sample size estimation, an OR between the two arms of 1.86 is assumed as a precaution. This assumption sets the proportion of patients who will obtain a favourable outcome in the control arm at 65% and the proportion of responders in the experimental arm at least 76%. These proportions may appear high, but it should be noted that the study does not include patients with early death and without surgery.

The experimental design includes two intermediate analyses; a sequential group test and the O'Brian-Fleming Analog spending function for alpha and beta errors were used.

Therefore set unilateral alpha at 0.025 and the power of the test (1-beta) at 0.80, 284 patients are needed per experimental arm; details are given in table 3 and figure 1.

A drop-out rate of no more than 10% is expected so that the sample size will be 630 patients (315 per experimental arm).

All estimates for the interim analyses are made without considering the inflation quota for drop-out patients. Therefore this evaluation will be made at the planned number of patients who completed the study. Only the final analysis will bear any inflationary share of the sample.

Table 3. Summary Report -

Item	Value
Maximum Number of Stages (Design):	3
Current Stage:	0
Alternative Hypothesis:	$P1 - P2 < 0$ (one-sided)
Alpha Spending Function:	O'Brien-Fleming Analog
Beta Spending Function:	O'Brien-Fleming Analog
Futility Boundaries:	Binding
Target Alpha:	0.025
Alpha (from simulations):	0.025
P1:	0.65
P2:	0.76
N1 (if final stage reached):	284
N2 (if final stage reached):	284
Target Power:	0.8
Power (from simulations):	0.8016
Maximum Information:	692.8

Information Report

Maximum Information: 692.8519

 Alternative Hypothesis: $P1 - P2 < 0$ (one-sided)

Alpha: 0.0250

Stage	Target information proportion	Target sample size N1	Target sample size N2	P1	P2
1	0.33	95	95	0.65	0.76
2	0.67	189	189	0.65	0.76
3	1.00	284	284	0.65	0.76

Alpha Spending

Target Final Stage Alpha: 0.0250

Spending Function: O'Brien-Fleming Analog

Stage	Information proportion	Alpha spent this stage	Cumulative alpha spent	Percentage alpha spent at this stage	Cumulative percentage
1	0.33	0.0001	0.0001	0.4	0.4
2	0.67	0.0059	0.0060	23.8	24.2
3	1.00	0.0190	0.0250	75.8	100.0

Beta Spending for Futility

Target Cumulative Beta at Final Stage: 0.2000

Spending Function for Futility: O'Brien-Fleming Analog

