12.7 Interim analysis

The group-sequential study design provided two interim analyses when 190 and 378 patients completed the study. Figure 2 shows the stopping limits for the first interim analysis.

[figure not shown]

Figure 2.

Three conditions will be possible:

- Z-statistics in the favorable zone: stop for efficacy ($z \leq -3.710$)
- Z-statistics in the unfavorable zone: stop for futility ($z \geq 0.270$)
- Z-statistics in the promising zone ($-3.710 < z < 0.270$)

For the first interim analysis, only the conditions of futility and efficiency will be verified. A blinded statistical analysis of the study objective will be carried out and provided to the BMDC, which will advise on the continuation of the study.

Figure 3 shows the stopping limits and the conditions for adaptive re-estimation of the sample size for the second interim analysis.

[figure not shown]

Figure 3.

Three conditions will be possible:

- Z-statistics in the favorable zone: stop for efficacy ($z \leq -2.511$)
- Z-statistics in the unfavorable zone: stop for futility ($z \geq -1.224$)
- Z-statistics in the promising zone ($z > -2.511$ and < -1.224)

A blinded statistical analysis of the study objective will be carried out and provided to the IMDC, which will advise on the continuation of the study.

Regarding the possibility of falling into the promising zone and considering clinically valid increase in patients with a favourable outcome compared to the control arm of at least 8 percentage points (NNT@12), two simulations with 100,000 samples were performed.

First, given the sample size (630 patients), the response rate in the control group was from 0.68 to 0.70, and the response rate in the experimental group was fixed at 0.76; the boundary equal to -1.9308 as the O'Brian-Fleming expenditure function for the third interim analysis; solving then for beta (Table 4 shows the simulation plan).

Table 4. Simulation Design for the last look

Scenario	Power	N1	N2	Alpha	Responders control	Responders treatment
1	0.580	315	315	0.025	0.68	0.76
2	0.477	315	315	0.025	0.69	0.76
2	0.379	315	315	0.025	0.70	0.76

The second simulation, with the same sample size and the same boundary, but in this case, varying the response rate in the experimental group (from 0.76 to 0.70) and response rate in the control group fixed at 0.65 (Table 3 shows the simulation plane)

Table 4. Simulation Design for the last look

Scenario	Power	N1	N2	Alpha	Responders control	Responders treatment

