1	0.556	315	315	0.025	0.65	0.73
2	0.656	315	315	0.025	0.65	0.74
2	0.753	315	315	0.025	0.65	0.75

Should one of the scenarios occur, a new sample size estimate will be possible. A conditional power analysis for the emerging z-value will be performed and provided to the IDMC.

Independent Data Monitoring Committee (IDMC)

An independent Data Monitoring Committee (IDMC) will closely review the safety data and efficacy of the interim analysis and provide recommendations for the continuation of the study. The IDMC will be composed of at least three members, of which at least one will be a specialist in the domain of neurology and at least one in the domain of reanimation and a methodologist. The members of the IDMC will be appointed before the protocol is submitted to the ethics committee for final approbation.

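### The look-2 sample size re-estimation can be triggered by 6- and 7-point scenarios, below the protocol's own 8-point minimum, and the visible text does not secure one-sided alpha 0.025 after a change of N

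*Protocol*

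**What the plan says.** Section 12.5 of the protocol fixes the design: "Therefore set unilateral alpha at 0.025 and the power of the test (1-beta) at 0.80, 284 patients are needed per experimental arm". It assumes "the proportion of patients who will obtain a favourable outcome in the control arm at 65" per cent and "the proportion of responders in the experimental arm at least 76" per cent. For losses, "A drop-out rate of no more than 10% is expected so that the sample size will be 630 patients" (315 per arm). Its boundary table declares futility binding and gives a look-2 futility limit of -1.1224 and a final limit of -1.9308.

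Section 12.7 places look 2 at 378 completers (189 per arm). It gives the futility limit there as -1.224 and calls everything between it and -2.511 the promising zone. It introduces the re-estimation as meant for results in that zone, and its yardstick reads: "considering clinically valid increase in patients with a favourable outcome compared to the control arm of at least 8 percentage points (NNT@12". The scenarios, at 315 per arm, come in two sets:

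- First set: control 0.68, 0.69 and 0.70 against 0.76, that is 8, 7 and 6 points.
- Second set, as tabulated: 0.73, 0.74 and 0.75 against control 0.65, that is 8, 9 and 10 points. The prose gives the range for this set as 0.76 down to 0.70, which reaches 5 points.

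The rule is then: "Should one of the scenarios occur, a new sample size estimate will be possible". The conditions are said to be in Figure 3, which is missing from the text available. A conditional power analysis goes to the monitoring committee, with no threshold stated.

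**The concern.** A re-estimation rule says for which interim results the sponsor will pay for more patients. Here the paragraph that names 8 points as the smallest worthwhile gain also lists 7 and 6 points among the scenarios that open a larger trial. Read literally, the trial could be enlarged to establish an effect that the protocol does not regard as clinically valid.

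The second matter is the type I error. If N changes after the arms have been compared, an ordinary final statistic with an unchanged limit has no general guarantee of its nominal level. The limit of -1.9308 also takes credit for binding futility and belongs to 284 per arm. With no stated direction or ceiling for the change, the claimed 0.025 rests on choices that the visible text leaves open.

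**Working it through.** **Inputs.** 95, 189 and 284 per arm; efficacy limits 3.7103, 2.5111 and 1.9308; look-1 futility limit -0.2701; look-2 futility limit 1.1224 (section 12.5) or 1.224 (section 12.7). Signs are reversed from the protocol, so positive z favours cilostazol. All figures use a normal approximation and an unadjusted z.

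**Reproducing the plan.** Numerical integration of the three-stage process with the section 12.5 limits gives alpha 0.0250 and power 0.8025 (stated 0.8016). Information is 284 / (0.65×0.35 + 0.76×0.24) = 692.85, as stated. The design is sound as long as N does not change.

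**What the scenarios mean at look 2.** With n = 189, z = d / sqrt{[p1(1-p1) + p2(1-p2)]/189}. Conditional power at 284 per arm under the observed trend is 1 - Φ{(1.9308√284 - z×284/√189)/√95}. For 6 points, the standard error is sqrt(0.3924/189) = 0.0456, so z = 0.06/0.0456 = 1.32 (1.31 with pooled variance). Then (32.54 - 27.20)/9.75 = 0.55, which gives 29%.

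| Observed at look 2 | Gain (points) | z | Conditional power at 284 |
|---|---|---|---|
| 0.70 vs 0.76 | 6 | 1.32 | 29% |
| 0.69 vs 0.76 | 7 | 1.53 | 46% |
| 0.68 vs 0.76 | 8 | 1.74 | 64% |
| 0.65 vs 0.73 | 8 | 1.69 | 59% |
| 0.65 vs 0.75 | 10 | 2.13 | 88% |
| Zone edge, limit 1.1224 (control 65%) | 5.4 | 1.12 | 17% |
| Zone edge, limit 1.224 (control 65%) | 5.9 | 1.22 | 23% |

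The 5-point end of the prose range gives z = 0.05/0.0481 = 1.04, which is already past either futility limit. That scenario could not open a re-estimation if it were observed at look 2. The 6- and 7-point scenarios could.

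To show why a ceiling matters: if 80% conditional power were the target (an assumption, as the protocol states none), an observed 6 points would call for about 776 per arm.

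**Alpha after a change of N, ordinary test, limit 1.9308, futility obeyed.** Given z at look 2 and final size N per arm, the conditional error is A(z, N) = 1 - Φ{(1.9308√N - z√189)/√(N - 189)}. Two examples:

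- At z = 1.1224, A is 0.040 for N = 284 and 0.058 for N = 568, so enlarging a weak result raises it.
- At z = 2.2, A is 0.41 for N = 284 and 0.81 for N = 200, since (27.31 - 30.24)/3.32 = -0.89. Cutting N after a good result raises it far more.

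The table integrates A over the look-2 continuation region under the null, taking the least favourable N for each z, with increases capped at twice the base.

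| Look-2 futility limit | Base per arm | Increases only | N may fall to 230 | N may fall to 200 |
|---|---|---|---|---|
| 1.1224 | 284 | 0.0256 | 0.0290 | 0.0333 |
| 1.1224 | 315 | 0.0244 | 0.0290 | 0.0333 |
| 1.224 | 284 | 0.0244 | 0.0278 | 0.0321 |
| 1.224 | 315 | 0.0232 | 0.0278 | 0.0321 |

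Ordinary rules that raise N to reach 80% or 90% conditional power stay below 0.025. If increases are allowed only at z of 1.69 or more (about 8 points), the worst case is 0.0250, because a larger N no longer raises the conditional error there.

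**The case against.** An observed gain is not the true effect. At 6 points the 95% interval is 6 ± 1.96×4.56, about -3 to 15 points, which is compatible with both 8 and the design's 11. Continuing from such a result is reasonable, and the scenarios may have been meant as assumed rates for a power table. That stands as a reason to continue to the planned N. It does not remove the contradiction, because the text makes the scenarios themselves the condition for a new sample size.

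Three stronger readings are tempting and are not supported.

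- **That the protocol chooses an unweighted final test.** It does not say so. The limit -1.9308 enters section 12.7 as an input to simulations at the unchanged 630 patients, and the statistical analysis plan, which is not at hand, may name another statistic.
- **That re-estimation is open across the whole continuation region.** The zone's name suggests it, but the written trigger is one of the scenarios (z about -1.32 to -2.13 in the protocol's sign), and Figure 3 may narrow it further.
- **That alpha is 0.0284, or 0.0291 with worst-case increases as well.** These figures arise only if futility is not obeyed, and 0.0284 involves no re-estimation. Futility is declared binding. "The sponsor retains decision-making authority" in section 10.3.7 is general text on the monitoring board and does not make it non-binding.

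**Conclusion.** The contradiction in section 12.7 is firm: two of the six scenarios that open re-estimation fall below the 8-point minimum, and a missing figure cannot undo the written sentence. The alpha point is a missing guarantee, not a demonstrated large error. With futility obeyed and increases only, the worst case passes 0.025 in one of four combinations of futility limit and base size, and only by 0.0006. Inflation to about 0.028 to 0.033 requires N to be cut to 230 or 200 per arm. The visible text does not exclude a cut, but nothing suggests that one is intended.

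These results assume an ordinary pooled z with the limit -1.9308 retained, increases to at most twice the base, and the two illustrative lower bounds on N. Figure 3 or the statistical analysis plan could settle direction, cap and final test. Neither would reconcile the scenarios with the 8-point minimum, or -1.1224 in section 12.5 with -1.224 in section 12.7.

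**What to change.** 1. Make the triggers agree with the 8-point minimum: remove the 7- and 6-point scenarios, and align the prose range of the second set with its tabulated rows.
2. State that N may only be increased, and give the maximum.
3. After any change of N, use a final statistic with pre-fixed stage weights (Cui-Hung-Wang or inverse-normal), which keeps the planned alpha for any new N if futility is obeyed. Alternatively, limit increases to an observed gain of about 8 points or more, which alone holds the ordinary test at or below 0.0250.
4. Reconcile the look-2 futility limit between sections 12.5 and 12.7.

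This costs protocol wording, and it has to be settled before any comparative interim result is seen. Fixed weights lose a little efficiency. Restricting the trigger gives up some freedom to rescue a weak interim result: with control at 65% and a true 8-point gain, about 21% of trials would be in the zone at look 2 but below z = 1.69 (about 14% with a true 11-point gain). Those trials would still run to the planned size.

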13 QUALITY CONTROL AND ASSURANCE

Each biomedical research project managed by Le GHU Paris Psychiatrie et Neurosciences is ranked from A to D according to the projected risk incurred by research subjects using the classification of biomedical research sponsored by Le GHU Paris Psychiatrie et Neurosciences

13.1 General organisation

The sponsor must be responsible for the safety and respect of those subjects who have agreed to participate in the research. The sponsor must implement a quality assurance system to best monitor the conduct of the research in the investigation centres.

For this purpose, the sponsor shall delegate Clinical Research Associates (CRA) whose primary role is to carry out regular follow-up visits at the research locations, after having carried out initial visits.

The objectives of monitoring the research, as defined in the French Good Clinical Practices (BPC section 5.18.1), are to verify that:

- the rights, safety and protection of the research subjects are met
- the data reported is exact, complete and consistent with the source documents
- the research is carried out in accordance with the protocol in force, with the French GCPs and with the legislative and regulatory provisions in force

13.1.1 Strategy for opening the centres

The strategy for opening the centres established for this research is determined using the appropriate monitoring plan. All centres will be opened simultaneously.

13.1.2 Level of centre monitoring

In the case of this research, which is considered an intermediate risk, the appropriate monitoring level has been determined based on the complexity, the impact and the budget for the research. Thus, the sponsor and the coordinating investigator have agreed on the logistic score and impact, resulting in a research monitoring level to be implemented: level C.

Mandatory elements concerning patients' consent will be fully monitored. As the main endpoint is of primarily importance, its level of monitoring will be 100%. Considering a C level of risk, which is considered intermediate, the level of monitoring for the safety data will be 100%. Other data concerning secondary outcomes will be telemonitored and 25% will be monitored fully.

13.2 Quality control

A Clinical Research Associate (CRA) appointed by the sponsor will be responsible for the proper conduct of the research, for collecting and documenting, recording and reporting the data generated in writing, in accordance with the Standard Operating Procedures applied within the DRCI and in accordance with the French Good Clinical Practices as well as with the legislative and regulatory provisions in force.

The investigator and the members of the investigator's team agree to make themselves available during Quality Control visits carried out at regular intervals by the Clinical Research Associate. During these visits, the following elements will be reviewed:

- written consent
- compliance with the research protocol and with the procedures defined therein
- quality of the data collected in the case report form: accuracy, missing data, consistency of the data with the "source" documents (medical files, appointment books, original copies of laboratory results, etc.)
- management of the treatments used

13.3 Case Report Form

All information required according to the protocol must be entered in the case report forms. The data must be collected as and when they are obtained, and clearly recorded in these case report forms. Each missing data item must be coded.

This digital case report form will be implemented in each centre thanks to a web-based data collection medium. Investigators will be given a document offering guidance in using this tool. When the investigators complete the case report via the Internet, the CRA can view the data quickly and remotely. The investigator is responsible for the accuracy, quality and relevance of all the data entered. In addition, the data are immediately verified as they are entered, thanks to consistency checks. Thus, the investigator must validate any changes to the values in the case report form. These modifications will be subject to an audit trail. A justification can be added when applicable, as a comment. A print-out, authenticated (signed and dated) by the investigator, will be requested at the end of the research. The investigator must archive a copy of the authenticated document that was delivered to the sponsor.

13.4 Management of non-compliances

Any events that occur as a result of non-compliance, by the investigator or any other individual involved in conducting the research, with the protocol, with the standard operating procedures, with the good clinical practices or with the legislative and regulatory provisions in force must be noted in a declaration of non-compliance addressed to the sponsor. As a first step, major or critical non-compliances will be reviewed and processed by the DRCI's medical coordinator in order to implement the necessary corrective or preventive actions. Next, the non-compliances will be sent to the Quality - Risk Management Division of the DRCI for verification and analysis. These verifications could result in the investigator in charge of the research location in question being asked for information or could lead to compliance or audit visits.

13.5 Audits/inspections

The investigators agree to accept the quality assurance audits carried out by the sponsor as well as the inspections carried out by the competent authorities. All data, documents and reports may be subject to regulatory audits and inspections. Medical secrecy cannot be invoked in opposition to these audits and inspections.

An audit can be carried out at any time by individuals appointed by the sponsor and who are not associated with the research directors. The objective of the audit is to ensure the quality of the research, the validity of the results and compliance with the legislation and regulations in force.

The individuals who lead and monitor the research agree to comply with the sponsor's requirements and with the competent authority regarding research audits or inspections.

The audit may be applicable to all stages of the research, from the development of the protocol to the publication of the results and the organisation of the data used or produced as part of the research.

13.6 Primary investigator's commitment to assume responsibility

Before starting the research, each investigator will give the sponsor's representative a copy of his/her personal curriculum vitae, signed and dated, with his/her number in the RPPS (Répertoire Partagé des Professionnels de Santé, Collective Database of Health Professionals).

Each investigator will undertake to comply with the legislation and to carry out the research according to French GCP, adhering to the Declaration of Helsinki terms in force.

The primary investigator at each participating centre will sign a responsibility commitment (standard DRCI document) which will be sent to the sponsor's representative.

The investigators and their employees will sign a delegation of duties form specifying each person's role.

13.7 Pharmacist's commitment to assume responsibility

Each pharmacist will be responsible for the reception, the good storage and management of the experimental treatment according to the pharmacy manual (standard DRCI document). The employees of the parhamcy involve in the study, will sign a delegation of duties form specifying each person's role.

14 ETHICAL AND LEGAL CONSIDERATIONS

This research will also be conducted in accordance with European laws and regulations, the principles of the World Medical Association (WMA) Declaration of Helsinki, established by the 18th WMA Assembly (Helsinki, 1964) and subsequent amendments, and current ICH GCP guidelines. It will be registered in European Medicines Agency (EMA) databases and other sites as appropriate, including the US Food & Drug Administration (FDA - clinicaltrials.gov) clinical trials database

